### **9.5.2. Safety Analyses**

Safety analysis will be conducted using the safety population and summarized by treatment group. The treatment-emergent period will be defined as the period from initial exposure of the study drug through 48 weeks after treatment administration or the date of the initiation of another investigational agent or surgical intervention, whichever occurs first. Safety will be assessed through summaries of adverse events and clinical laboratory evaluations.

AEs will be coded using the latest version of Medical Dictionary for Regulatory Activities (MedDRA; version 21.0 or higher). All reported AEs (whether treatment emergent or not) will be included in by-patient AE listings. The severity of all adverse events will be evaluated by the investigator. The incidence of the adverse events will be presented by system organ class and preferred term, relationship to study treatment, and severity. Treatment emergent AESIs and treatment related AESIs will also be summarized by system organ class (SOC) and preferred term (PT). A list of all AESIs can be found in [Section 8.5.6](#).

Laboratory data will consist of chemistry, hematology, and urinalysis data. Only data collected by the laboratory will be included in the analysis.

Descriptive statistics of observed values and change from baseline for vital signs and post void residual volume will be listed and summarized.

Supplemental safety analyses will be performed to separate subjects that did or did not receive additional OAB treatment at or after Week 24. Tables that are to be repeated with the alternative safety population will be described further in the SAP.

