Study visits will be identical for Cohorts 1 and 2. Subjects will be evaluated during a 5-week screening and randomization period for eligibility (Days -35 to -1). Eligible subjects will be randomized to treatment at the Randomization Visit (Visit 2) within each cohort; however, subjects will be administered the study treatment via cystoscopy on Day 1 (Visit 3). All subjects will be evaluated at scheduled post-treatment clinic visits at Weeks 2, 6, 12, 18, and 24 (Visits 4 to 8, respectively), or until the subject exits the study. Week 18 may be conducted by phone or other virtual technology. Afterwards, 2 follow-up visits by phone or other virtual technology will be performed at Week 36 (Visit 9) and Week 48 (Visit 10) for subjects who have completed the Week 24 Visit.

Starting at Week 24 (Visit 8), subjects can request and receive additional OAB treatment(s) at the clinical discretion of the investigator. Subjects who receive additional OAB treatment(s) at Week 24 or after will only be followed to assess adverse events at any future telephone (or other virtual technology) visits (Week 36 and/or Week 48). No bladder diaries will be collected, and no efficacy assessments will be performed once a subject receives an additional OAB treatment.

Refer to Section 1.3 of the protocol for a detailed time and events schedule. Study schema is shown below:

Figure 1: Schematic of Study Design: 2-Cohort, Dose-Escalation

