5.4.1. Additional OAB Treatment

Starting at Week 24 and after (at clinic visit, phone visits or between visits), subjects can request and be prescribed additional OAB treatment(s). A treatment is considered additional OAB treatment if on the “Concomitant Medications/Procedures” eCRF the answer to “Is this an additional OAB medication” is “Yes”, regardless of when the additional OAB treatment was received.

The additional OAB medication will be summarized by ATC level 2, 4, and Preferred Term while additional OAB procedures will be summarized by preferred term. Separate listings for additional OAB medications and procedures will be provided.

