7.1. Extent of Exposure and Compliance

Since this is a treatment with single injection at the start of the study, no summary of exposure or compliance will be provided. A listing of study injection will be provided for all subjects in the safety population.

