7.2. Adverse Events

Adverse events (AEs) will be coded using MedDRA version 22.1. or later.

All reported AEs (whether treatment emergent or not) will be included in by-subject AE listings. Sorting will be by treatment, subject, date of event, SOC, PT and then verbatim description.

An AE will be considered a treatment emergent adverse event (TEAE) if it begins or worsens in severity after initial exposure of the study treatment through 48 weeks after treatment administration or the date of the initiation of another OAB medication, investigational agent or surgical intervention, whichever occurs first. The determination of "48 weeks" will be based on the study day of the AE start date instead of the visit date of the Week 48 visit. The OAB medication will be determined based on the checkbox "Is this an additional OAB medication"

on the concomitant medication CRF. After data are collected and reviewed by the clinical team, a blinded list of investigational agents and surgical interventions will be provided to the programming team prior to database lock to determine which AEs should no longer be considered treatment emergent due to possible confounding effects. Partial AE start dates will be imputed as detailed in [Section 4.2.3](#).

Summary tables will be based on TEAEs. The incidence of TEAEs will be presented using counts and percentages of subjects with TEAEs and tabulated by SOC and PT. SOC will be sorted in descending frequency and PT within SOC will be sorted by descending frequency based on the incidence of all subjects treated with URO-902 included in the summary. If a subject has multiple occurrences (start and stop) of an event associated with a specific SOC or PT within a SOC, a subject will only be counted once in the incidence count for the SOC or PT within SOC respectively.

An overall summary table of AEs by treatment group will be presented detailing the number and percentage of subjects, and number of events for the following categories:

- At least one TEAE;
- At least one Treatment-Related TEAE;
- At least one Grade ≥ 3 TEAE (Mild = Grade 1, Moderate = Grade 2, Severe = Grade 3, Life-Threatening = Grade 4, Death = Grade 5)
- At least one Grade ≥ 3 Treatment-Related TEAE;
- At least one Serious TEAE;
- At least one Serious Treatment-Related TEAE;
- At least one TEAE leading to Discontinuation from Study;
- At least one TEAE of Special Interest;
- At least one Treatment-Related TEAE of Special Interest

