9. CHANGE FROM ANALYSIS PLANNED IN PROTOCOL

[figure not shown]
Protocol section 9.3 defined analyses population. In the SAP [Section 3.1](#), safety (modified) population was removed.

Protocol section 3.2.1 defined exploratory efficacy endpoints. In the SAP [Section 1.1.1](#) and [Section 4.3.2](#) , ‘Nighttime voids’ was added as an exploratory efficacy endpoint.

In the SAP [Section 7.2](#) the definition of treatment-emergent adverse event was updated to include the additional OAB medication as the end of the treatment-emergent period in addition to the initiation of the investigational agent and/or surgical intervention.

In Protocol section 9.5.1 PGI-C change from baseline was analyzed using MMRM method. In the SAP section 4.3.3 and 6.2 the analysis method for PGI-C was changed to use the responder analysis with CMH method.

SAP added additional endpoint of proportion of subjects achieving $\geq 50\%$, $\geq 75\%$ and 100% reduction in average daily UI episodes.

Since no analysis plan is definitive especially for this exploratory study, we may perform additional data driven sensitivity analysis.

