14.3.1.2.1	Treatment-Emergent Adverse Events by System Organ Class and Preferred Term	Safety	Sort by SOC and PT in descending frequency of URO-902 arms combined.	TL, EOS
14.3.1.2.2	Treatment-Emergent Adverse Events Occurring between Weeks 1 and 24 by System Organ Class and Preferred Term	Safety	Sort by SOC and PT in descending frequency of URO-902 arms combined.	EOS
14.3.1.2.3	Treatment-Emergent Adverse Events Occurring between Weeks 24 and 48 by System Organ Class and Preferred Term	Safety	Sort by SOC and PT in descending frequency of URO-902 arms combined.	EOS
14.3.1.3.1	Treatment-Emergent Adverse Events by Preferred Term	Safety	Sort by PT in descending frequency of URO-902 arms combined. Same for all subsequent tables	TL, EOS
14.3.1.3.2	Treatment-Related Treatment-Emergent Adverse Events by Preferred Term	Safety		EOS

Title		Population	Programming Note	Deliverable
14.3.1.4	Treatment-Emergent Adverse Events by Preferred Term and Maximum Intensity	Safety		EOS
14.3.1.5	Treatment-Emergent Adverse Events with Grade ≥ 3 by Preferred Term	Safety		EOS
14.3.1.6	Treatment-Related Treatment-Emergent Adverse Events with Grade ≥ 3 by Preferred Term	Safety		EOS
14.3.1.7	Serious Treatment-Emergent Adverse Events by Preferred Term	Safety		TL, EOS
14.3.1.8	Treatment-Related Serious Treatment-Emergent Adverse Events by Preferred Term	Safety		EOS
14.3.1.9	Fatal Treatment-Emergent Adverse Events by Preferred Term	Safety		EOS
14.3.1.10	Treatment-Emergent Adverse Events Leading to Study Discontinuation by Preferred Term	Safety		TL, EOS
14.3.1.11	Treatment-Emergent Adverse Events of Special Interest by Preferred Term	Safety		EOS
14.3.1.12	Treatment-Related Treatment-Emergent Adverse Events of Special Interest by Preferred Term	Safety		EOS
14.3.1.13	Non-Fatal Serious Treatment-Emergent Adverse Events by Preferred Term	Safety		EOS
14.3.1.14	Adverse Events Occurred After Study Dose Through Week 48 and After Initiation of Another OAB Medication, Investigational Agent, or Surgical Intervention	Safety	Same Layout as the Overall AE Summary Table 14.3.1.1	EOS
14.3.2.6	List of Deaths	Safety		EOS
14.3.2.7	Listing of Serious Adverse Events	Safety		EOS
14.3.2.8	Listing of Treatment-Emergent Adverse Events Leading to Study Discontinuation	Safety		EOS

Title		Population	Programming Note	Deliverable
14.3.2.9	Listing of Treatment-Emergent Adverse Events of Special Interest	Safety		EOS
Laboratory data				
14.3.3.1	Hematology Laboratory Parameters	Safety	Include observed and CFB	EOS

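### The SAP stops counting treatment-emergent events when additional OAB medication starts but reports crude percentages, which pushes late-period figures down in whichever arm uses more of it

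*SAP*

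**What the plan says.** Both documents set the safety objective at up to 48 weeks after a single dose, but they define the treatment-emergent period differently.

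- Protocol 9.5.2 runs it "through 48 weeks after treatment administration or the date of the initiation of another investigational agent or surgical intervention, whichever occurs first". OAB medication does not end it.
- SAP 7.2 adds OAB medication to the list: "or the date of the initiation of another OAB medication, investigational agent or surgical intervention, whichever occurs first". SAP 9 declares the change: "the definition of treatment-emergent adverse event was updated to include the additional OAB medication as the end of the treatment-emergent period".
- On the measure, SAP 7.2 says: "The incidence of TEAEs will be presented using counts and percentages of subjects with TEAEs and tabulated by SOC and PT". SAP 7.1 says "no summary of exposure or compliance will be provided", and no person-time rate is planned anywhere.
- On timing, SAP 1.2.1 says: "Starting at Week 24 (Visit 8), subjects can request and receive additional OAB treatment(s) at the clinical discretion of the investigator". SAP 5.4.1 counts any treatment flagged on the form, "regardless of when the additional OAB treatment was received", so earlier use would also close the window.
- SAP 11.1.1 plans a Weeks 1-24 table (14.3.1.2.2) and a second, 14.3.1.2.3: "Treatment-Emergent Adverse Events Occurring between Weeks 24 and 48 by System Organ Class and Preferred Term".
- Events after additional OAB medication, an investigational agent or surgery go to Table 14.3.1.14, which has the layout of the overall table and no preferred terms.
- The listing of events of special interest (14.3.2.9) covers treatment-emergent events only. Serious events, deaths and all adverse events are listed in full.
- Protocol 9.5.2 promised supplemental analyses separating subjects with and without additional OAB treatment. SAP 9 drops the safety (modified) population, and no table in SAP 11.1.1 splits the adverse event summaries by that status.

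**The concern.** Additional treatment starts at the subject's request (protocol 6.9.2), so it plausibly follows lack of benefit. If the drug works, placebo subjects may take more of it and lose more counted follow-up. A crude percentage treats a subject watched for 24 weeks like one watched for 48. Placebo would then look safer late on, and the active arms relatively worse, with no difference in true risk. The Weeks 1-24 table is largely free of this, but it says nothing about late events after a single gene-therapy injection. The excluded events are collected, because adverse event follow-up continues after additional treatment. What is lost is their place in the by-term comparison.

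**Working it through.** **Inputs.** Neither document gives a rate of additional medication, an adverse event rate or a precision for safety, so there is no plan figure to reproduce. From the documents: use allowed from Week 24, a 48-week window, and 26 subjects per group once placebo is pooled (SAP 1.2.3 and 1.2.4), so one subject is 1/26 = 3.8 points. Assumed: the same constant hazard h in both arms; the proportion u starting additional medication; and a 48-week incidence of 30% or 50%.

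**Overall 48-week table.** Let F(t) = 1 − exp(−ht). If a proportion u starts at Week 24, the crude percentage is (1 − u)F(48) + uF(24). If start dates are spread evenly over Weeks 24-48, F(24) is replaced by the mean of F(t) over that interval. For 50% incidence, F(24) = 1 − √0.5 = 29.3%; for 30%, F(24) = 1 − √0.7 = 16.3%. Example at 50%, u = 20% v 50%: 0.8 × 50 + 0.2 × 29.3 = 45.9%, against 0.5 × 50 + 0.5 × 29.3 = 39.6%.

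Percentages, less-medicated v more-medicated arm (gap in points, from unrounded values):

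| Incidence, start of medication | u = 10% v 30% | u = 20% v 50% | u = 20% v 60% |
|---|---|---|---|
| 30%, Week 24 | 28.6 v 25.9 (2.7) | 27.3 v 23.2 (4.1) | 27.3 v 21.8 (5.5) |
| 30%, spread | 29.3 v 28.0 (1.3) | 28.7 v 26.7 (2.0) | 28.7 v 26.0 (2.7) |
| 50%, Week 24 | 47.9 v 43.8 (4.1) | 45.9 v 39.6 (6.2) | 45.9 v 37.6 (8.3) |
| 50%, spread | 49.0 v 47.1 (2.0) | 48.0 v 45.1 (2.9) | 48.0 v 44.1 (3.9) |

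If events cluster early, so that only a share g of first events falls after Week 24, the gap for starts at Week 24 is incidence × g × difference in u. At 50% incidence and g = 10% to 20%, that is 1.0 to 4.0 points.

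**Weeks 24-48 table, full safety denominator.** Assume a true risk of 30% over those weeks in both arms.

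- 50% v 25% start at Week 24: 0.50 × 30 = 15.0% v 0.75 × 30 = 22.5%, ratio 1.50.
- The same proportions spread evenly: a subject who starts has mean counted risk 1 − 0.3/(−ln 0.7) = 15.9%. This gives 0.5 × 30 + 0.5 × 15.9 = 22.9% v 0.75 × 30 + 0.25 × 15.9 = 26.5%, ratio 1.15.
- 60% v 20% at Week 24: 12% v 24%, ratio 2.0.
- Equal u in both arms: ratio 1.0.

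**Does a rate remove it?** Under a constant hazard, expected time at risk to first event equals crude incidence divided by h. At 50% incidence h = ln 2/48 = 0.01444 per week. With u = 20% v 50% the crude 45.9% and 39.6% both become 1.44 first events per 100 subject-weeks.

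**Can the protocol-window figure be rebuilt?** By-term tables 14.3.1.2.1 to 14.3.1.13 hold treatment-emergent events only. Table 14.3.1.14 has no terms. If it holds only events after the cut-off, a subject with events on both sides appears in both sets, and the two counts cannot be added. By-term incidence to Week 48 would have to be rebuilt from listings.

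**The case against.** The case for the SAP has weight.

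- **The change is declared and has a purpose.** SAP 7.2 cites possible confounding for investigational agents and surgery, and the protocol already truncates at both. Botulinum toxin is no longer prohibited from Week 24 (protocol 6.9.1 and 10.7). Protocol 2.1 associates onabotulinumtoxinA with urinary tract infection and retention, which are this study's events of special interest. Counting everything to Week 48 in the main tables could inflate those events on placebo and hide a drug signal. This stands: neither version is free of bias, so replacing the main definition is not clearly better.
- **A reader might infer that the more-medicated arm will show fewer events whatever the drug does.** The documents do not support that. A true hazard ratio of about 1.13 to 1.31 in that arm cancels the 48-week shift over the scenarios above (starts at Week 24). At equal hazards with 26 per arm, 50% incidence and u = 20% v 50%, that arm shows a strictly lower percentage in only about 62% of trials.
- **A reader might also infer that late serious events disappear.** They do not. Table 14.3.1.14 has rows for serious and special-interest events, serious events and deaths have full listings, and every event is listed with its emergent status. Unequal use will show in the disposition table and Tables 14.1.5.3 to 14.1.5.6.
- **The ratios depend on an unstated denominator.** SAP 4.2.2 refers to subjects with available data, and nothing specific is given for Table 14.3.1.2.3. With subjects still at risk at Week 24 as denominator, starts at Week 24 would give 30% v 30%. That removes only the part due to starts at Week 24: if starts are spread later, everyone is at risk at Week 24 and the 1.15 remains.
- **Safety is descriptive, and the Week 36 and 48 visits are remote.** Events defined by residual volume or culture are less likely to be detected then. This limits the size of the problem, but a descriptive percentage over unequal follow-up can still mislead.

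**Conclusion.** The point holds as a conditional bias in the late-period tables. If additional OAB medication is commoner in one arm, the plan as written lowers that arm's crude percentages. With equal true hazards, 48-week incidence of 30% to 50% and the assumed imbalances, the gap is about 1 to 8 points over 48 weeks, or roughly a fraction of one subject to two subjects in 26. In the Weeks 24-48 table the ratio is about 1.15 to 2.0 on the full safety denominator. The gap is nil if use is balanced and small if events occur early. The rates of additional medication and of events are assumptions, and the direction against active drug rests on placebo subjects taking more.

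Separately, and whatever those rates are, the planned tables do not allow by-term incidence over the protocol window to be recovered. The documents do not support saying that the SAP conceals late events or that its cut-off is wrong in itself. This is an inexpensive improvement to the safety reporting.

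**What to change.** Keep the SAP cut-off for the main tables if preferred, and make four changes.

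1. Add exposure-adjusted rates (subjects with a first event per 100 subject-weeks at risk) to the overall and Weeks 24-48 tables of treatment-emergent, serious and special-interest events. Show the Weeks 24-48 rate on its own: a single 48-week rate assumes a constant hazard and would itself mislead if events cluster after the injection.
2. Add a supplementary by-preferred-term table of all adverse, serious and special-interest events through Week 48 regardless of OAB medication, using the protocol 9.5.2 window.
3. State the denominator of Table 14.3.1.2.3.
4. State whether Table 14.3.1.14 counts only events after the cut-off or all events to Week 48.

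The cost is SAP wording and a few more tables, with no new data. The drawback is that the all-events version includes events possibly caused by the additional treatment, so it should be labelled as such and read beside the cut-off version.

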### 6.9.2. Permitted Treatments

With the exception of the agents described in [Section 10.7](#), any other concomitant medication deemed necessary for the welfare of the subject during the study may be given at the discretion of the investigator. If the permissibility of a specific medication/drug is in question, please contact the Sponsor's designated Medical Monitor. Any medication or vaccine (including over-the-counter or prescription medicines, vitamins, and/or herbal supplements) that the subject is receiving at the time of enrollment, start of screening, or receives during the study must be recorded in the eCRF.

Furthermore, starting at Week 24 and after (at clinic visit, phone [or other virtual technology] visits or between visits), subjects can request and receive additional OAB treatment(s) such as those listed in [Section 10.7](#) (see [Section 6.9.1](#)) at the clinical discretion of the investigator. The following criteria should be followed in order for subjects to receive additional OAB treatment(s):

- Subject initiates a request for additional OAB treatment
- Ensure subject's last available OAB symptoms are recorded, as determined by the most recent 3-day patient Bladder Diary (if not already recorded)
- Investigator deems the additional OAB treatment is appropriate and that no condition or situation exists which, in the investigator's opinion, puts the subject at significant risk from treatment.

Subjects who receive additional OAB treatment(s) at Week 24 or after will only be followed to assess adverse events at any future telephone (or other virtual technology) visits (Week 36 and/or Week 48). No bladder diaries will be collected, and no efficacy assessments will be performed once a subject receives additional OAB treatment.

Additional OAB medications will not be provided by the Sponsor.

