Except for all TEAEs which will be summarized by SOC and PT, the incidence of all other TEAEs by PT will be presented for the following in descending frequency based on the incidence of all subjects treated with URO-902.

- All TEAEs by SOC and PT;
- All TEAEs
- Treatment-related TEAEs (i.e., Possibly Related or Probably Related);
- All TEAEs by PT, and maximum severity (where the maximum intensity per subject will be counted at each level of summarization);
- TEAEs with Grade ≥ 3 ;

- Treatment-related TEAEs with Grade ≥ 3 ;
- Serious TEAEs;
- Treatment-related serious TEAEs;
- Fatal TEAE;
- TEAEs leading to discontinuation from study;
- TEAE of Special Interest;
- Treatment-related TEAE of Special Interest;
- Non-fatal serious TEAE;

An AE is considered an AE of Special Interest if on the AE eCRF the answer to the item “Is this an AE of Special Interest?” is “Yes”. For specific criteria used to identify AEs of Special Interest refer to section 8.5.6 of the protocol.

Overall AE listing will include the treatment arm, start and stop dates/times of the AE, treatment dates/times, and treatment emergent status.

A Treatment related AE is defined as an AE for which the investigator classifies the AE as being “Possibly Related” or “Probably Related” to study treatment on Adverse Event eCRF. Missing relationship and severity (intensity) will be imputed per [Section 4.2.3](#).

Additional summary table will be provided for AEs that occurred on or after the study dose through 48 weeks after the study dose administration and after additional OAB medication was taken, or initiation of investigational agent, or surgical intervention.

The following additional listings will be provided:

- Listing of deaths
- Listing of SAEs
- Listing of TEAEs of Special Interest
- Listing of TEAEs leading to study discontinuation

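### SAP 7.2 stops every preferred-term adverse event table at the first additional OAB medication, investigational agent or listed surgery, so 48-week incidence by arm can be understated, chiefly for non-serious UTI

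*SAP*

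**What the plan says.** SAP 7.2 counts an AE as treatment-emergent if it starts or gets worse after dosing, up to 48 weeks "or the date of the initiation of another OAB medication, investigational agent or surgical intervention, whichever occurs first". OAB medication is identified by a checkbox on the concomitant medication form, and SAP 5.4.1 applies that flag "regardless of when the additional OAB treatment was received". The agents and surgeries that close the period come from a list drawn up blind before database lock. AE summary tables are then based on treatment-emergent AEs (TEAEs).

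Protocol 9.5.2 already had two of the three closing events. It ended the period at 48 weeks or "the date of the initiation of another investigational agent or surgical intervention, whichever occurs first". SAP 9 discloses the third: "the definition of treatment-emergent adverse event was updated to include the additional OAB medication as the end of the treatment-emergent period". Protocol 9.5.2 also planned a split: "Supplemental safety analyses will be performed to separate subjects that did or did not receive additional OAB treatment at or after Week 24". SAP 9 records that the "safety (modified) population was removed".

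AE collection does not stop at additional treatment. Protocol 6.9.2 says: "Subjects who receive additional OAB treatment(s) at Week 24 or after will only be followed to assess adverse events", at the remaining telephone or virtual visits. SAP 7.2 adds one summary that reaches past the cut-off, for AEs from dosing "through 48 weeks after the study dose administration and after additional OAB medication was taken, or initiation of investigational agent, or surgical intervention". This is Table 14.3.1.14, which SAP 11.1.1 gives the layout of the overall table 14.3.1.1.

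**The concern.** The safety objective (SAP 1.1.2) compares each dose with placebo up to 48 weeks after one injection that cannot be withdrawn. Taking another OAB drug does not end a woman's exposure to URO-902. It does end her contribution of new events to the tables that name the event.

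The closing event happens after randomization and may depend on treatment, since women whose symptoms persist or return have more reason to ask for another drug. SAP 7.1 plans no exposure summary, so the percentages take no account of a shortened window. What is at stake is late incidence by preferred term: it can be too low, and the comparison between arms can shift in either direction.

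**Working it through.** **1. Which outputs reach past a closing event (SAP 7.2 and 11.1.1)**

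| Output | Past the cut-off? | By preferred term? |
|---|---|---|
| 14.3.1.2.1 to 14.3.1.13 (include serious, fatal, Grade 3 or higher, AESI, and Weeks 24 to 48) | No | Yes |
| 14.3.1.14 | Yes | No: nine category rows, with both AESIs in one row |
| AESI listing 14.3.2.9 | No | By subject |
| All-AE listing 16.2.3.2, deaths 14.3.2.6, SAEs 14.3.2.7 | Yes | By subject |
| PVR 14.3.7 (maximum value), CIC 14.3.8 | Yes | Not AE tables |

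No planned table gives serious, Grade 3 or higher, or AESI incidence by preferred term and arm over 48 weeks regardless of closing events. Only a subject whose first onset or worsening of a term falls after the closing event is missed. A subject already counted for that term stays counted.

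**2. Can Table 14.3.1.14 fill the gap?** Its wording can mean only AEs after the closing event, or all AEs through 48 weeks. On neither reading does it show preferred terms. On the first, its subject counts cannot be added to 14.3.1.1. With an assumed 2 AESI subjects in each table, the 48-week count lies between max(2, 2) = 2 and 2 + 2 = 4, which is 2/26 = 7.7% to 4/26 = 15.4%, until the listings are checked.

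**3. Group size.** The plan gives no figure for this issue itself. SAP 1.2.4 gives 23 evaluable per group and about 10% attrition: 23/0.90 = 25.6, so 26 per group and 3 × 26 = 78, as stated. One omitted subject is 1/26 = 3.8 points.

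**4. Follow-up outside the preferred-term tables.** Assume k of 26 women in an arm start OAB medication at Week 24, with no dropout. The share of Weeks 24 to 48 lost is k/26. The share of 48 weeks lost is (k/26) × (24/48).

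| k (assumed) | Weeks 24 to 48 | All 48 weeks |
|---|---|---|
| 3 | 11.5% | 5.8% |
| 8 | 30.8% | 15.4% |
| 13 | 50.0% | 25.0% |

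Share of follow-up is not share of events, so step 5 adds an event model.

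**5. Effect on a displayed incidence.** Assume a true 48-week risk R = 10% at constant hazard, with a fraction q closing at Week 24 independently of risk. The risk by Week 24 is 1 − 0.90^(24/48) = 5.13%. The displayed risk is q × 5.13% + (1 − q) × 10%.

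| q (assumed) | Displayed | Affected subjects not counted |
|---|---|---|
| 10% | 9.5% | 5% |
| 25% | 8.8% | 12% |
| 50% | 7.6% | 24% |
| 75% | 6.3% | 37% |

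At q = 50% the uncounted share changes little with R: 24.7% at R = 5% and 23.6% at R = 20%. If closure comes at Week 36 instead, it is 12.0% (R = 10%).

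**6. Unequal closure.** With equal true risk of 10%, q = 25% on active and 50% on placebo displays 8.8% against 7.6%, a ratio of 1.16. Reversing the two gives 0.86.

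**The case against.** The cut-off is disclosed and has a reason. SAP 7.2 cites possible confounding for the agent and surgery list, and two of the three closing events come from the protocol. Protocol 2.1 associates onabotulinumtoxinA with UTI and urinary retention, this trial's two AESIs, and Protocol 6.9 allows it from Week 24. A table ignoring closing events would mix events caused by later therapy with those of the study drug. This stands, and it is why the TEAE tables should be kept and later events flagged.

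Retention is also well covered elsewhere. Protocol 8.5.6 records it only when a raised PVR needs catheterization, and Protocol 8.4.5 requires a retention AE when CIC is started. SAP 7.8 summarizes CIC by arm with no treatment-emergent cut-off, and SAP 7.7 takes maximum PVR from any post-baseline value. This stands too, although the later visits are by telephone or virtual, so a PVR after Week 24 depends on a further clinic attendance.

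The SAE and death listings are not limited to TEAEs and can be counted by hand in 78 subjects. Death is Grade 5, so it falls within the Grade 3 or higher row of 14.3.1.14. Listed OAB treatments are prohibited until Week 24, so the first half of follow-up should be largely intact. No dipstick is scheduled after Week 24, and a protocol-defined UTI needs a culture and leukocyturia, so late UTIs would come mainly from unscheduled care. These points shrink the gap but do not close it. A non-serious UTI after a closing event can be identified by term only in the all-AE listing.

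Removing the safety (modified) population is not clearly a loss. It excluded whole subjects, while the SAP keeps their AEs before the closing event.

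**Conclusion.** The point holds as a minor gap in tabulation. AEs that start or worsen after a closing event enter no preferred-term table, so preferred-term incidence by arm over the 48-week horizon can be understated, possibly unequally by arm. The gap matters most for non-serious AESIs, chiefly UTI. Its size is unknown: the documents give neither the rate of closing events nor the risk of late AEs, and every percentage in steps 4 to 6 of the working rests on assumed inputs.

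A reader might infer more than the documents support:
- That late events are lost or concealed. They are collected, listed by subject and counted by category, and the change is declared in SAP 9.
- That retention and UTI cannot be told apart by arm after a closing event. The CIC and PVR summaries track retention closely.
- That any additional OAB treatment closes the period. SAP 7.2 names OAB medication, identified by the checkbox, and listed surgery; a non-surgical OAB procedure does not clearly close it.

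**What to change.** Keep the SAP definition of a TEAE and all tables built on it. In SAP 7.2 and 11.1.1:
- Add three tables by preferred term and arm (serious, Grade 3 or higher including fatal, and AESI) for all AEs that start or worsen from dosing through 48 weeks, regardless of closing events.
- Flag events that start or worsen after a closing event, so both views can be read together.
- Do not restrict the AESI listing (14.3.2.9) to TEAEs.

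The cost is about three repeat tables and one wider listing from data already collected, with no change to trial conduct, sample size or power. The downside is that some events caused by later OAB therapy, such as onabotulinumtoxinA, will be counted, perhaps unequally by arm. The flag lets the reader see them.
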